#### 9.4. Definition of Evaluable Subjects, On Study, and End of Study

Section 15.2 indirectly addresses the definition of evaluable patients. All eligible patients who initiate checkpoint treatment will be followed for survival regardless of compliance to assigned treatment. In addition, all patients who initiate checkpoint treatment will be included in the denominator for assessing feasibility, whether or not a surgery occurs.

Participants will be considered on study once they have signed the informed consent form and eligibility has been confirmed. The study will be ended once all subjects have completed follow up and all data analysis is complete.

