### **12.6.3. Replacement of Early Withdrawal(s)**

Subjects who withdraw from the study without receiving both nivolumab and ipilimumab will be considered non-evaluable; those subjects will be replaced.

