#### **15.5.1.2. Continuous Monitoring of Feasibility and Analysis**

The proportion of patients experiencing surgical delay as defined in Section 15.5.1.1 will be computed as the number of patients with delayed surgery or whom never have surgery as a direct or indirect result of ipilimumab and/or nivolumab treatment divided by the total number of patients.

Neoadjuvant treatment patients who have delayed surgery or no surgery due to reasons unrelated to ipilimumab and/or nivolumab treatment will be excluded from the assessment of feasibility. However, this patient will be included in all other analyses if data is available. Reasons for such exclusions will be tabulated. All other patients will be considered evaluable for the assessment of feasibility.

Methods developed for continuous monitoring of toxicity will assess whether the number of surgical delays is not excessive. Based upon the Pocock boundary, the following monitoring rules were developed assuming that a true surgical delay rate of 10% is acceptable, and a surgical delay rate of 20% is too high. Accrual of patients will be suspended if the following conditions are satisfied:

# of Patients Enrolled to Date	Suspend Treatment Assignment if
1 – 4	# Evaluable Patients with Delayed Surgery > 1
5 – 8	# Evaluable Patients with Delayed Surgery > 2
6 – 14	# Evaluable Patients with Delayed Surgery > 3
15+	# Evaluable Patients with Delayed Surgery > 4

These monitoring rules were generated using the R software package. Specifically, the toxbdry function in the clinfun package (<https://cran.r-project.org/web/packages/clinfun/clinfun.pdf>) that implements methods developed by Jennison and Turnbull [20] and Ivanova et al [21] was used.

If accrual is suspended, the reasons for delay will be carefully reviewed to determine whether accrual should continue without any protocol modification, be permanently terminated, or whether modifications to the treatment regimen (e.g., removal of ipilimumab from the treatment regimen) should occur.

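### The surgical-delay suspension table contradicts itself at 6, 7 or 8 patients with exactly 3 delays, and it selects the row by enrolled patients while counting delays among evaluable ones

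*Combined protocol and SAP*

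**What the plan says.** Section 15.5.1.2 introduces the table with "Accrual of patients will be suspended if the following conditions are satisfied". The limits are described as Pocock-type, produced by the toxbdry function in R, on the premise that "a true surgical delay rate of 10% is acceptable, and a surgical delay rate of 20% is too high". As printed:

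| Patients (row label) | Suspend if delays exceed |
|---|---|
| 1–4 | 1 |
| 5–8 | 2 |
| 6–14 | 3 |
| 15+ | 4 |

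The row label is the number "of Patients Enrolled to Date". The condition in the third row is "Evaluable Patients with Delayed Surgery > 3", and the other rows have the same form.

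Four statements bear on who is enrolled and who is evaluable:

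- Section 9.4: "Participants will be considered on study once they have signed the informed consent form and eligibility has been confirmed".
- Section 12.6.3: patients who withdraw "without receiving both nivolumab and ipilimumab will be considered non-evaluable; those subjects will be replaced".
- Section 15.5.1.2: patients whose surgery is late or does not happen "due to reasons unrelated to ipilimumab and/or nivolumab treatment will be excluded from the assessment of feasibility". All remaining patients are evaluable.
- Section 9.4 again: "all patients who initiate checkpoint treatment will be included in the denominator for assessing feasibility, whether or not a surgery occurs".

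**The concern.** The table serves primary objective #1 and must give one answer for any state of the data. It fails to do so in three ways.

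1. **Overlapping rows.** Counts of 6, 7 and 8 fall in both the second and the third row. With exactly 3 delays, one row suspends and the other continues. The introductory sentence does not say whether one satisfied row is enough or whether the later row replaces the earlier one.
2. **Two different counts.** The row is selected by enrolled patients, but the delays are counted among evaluable patients. Enrolled is never smaller than evaluable, and the limits rise with the row, so a gap can only leave the limit unchanged or loosen it.
3. **No single feasibility population.** Section 9.4 keeps every patient who starts treatment. Section 15.5.1.2 drops those whose delay or missed surgery is unrelated to the drugs.

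Two people with the same data could therefore reach opposite decisions early in a 20-patient trial, when a suspension rule has most to offer.

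**Working it through.** **Inputs.** Acceptable rate 10%, unacceptable rate 20% and the printed limits (Section 15.5.1.2); up to 20 patients (Section 9.1). The 30% rate is added for illustration. The toxbdry arguments and the target crossing probability are not given, and toxbdry was not run, so only the shape of the boundary can be checked.

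**Step 1: does the stated method explain the table?** A Pocock-type rule applies one constant per-look level c. At n patients it suspends at the smallest x with P(X ≥ x | n, 0.10) ≤ c. The relevant binomial tails at 10% are:

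| n | x | P(X ≥ x) |
|---|---|---|
| 4 | 2 | 0.0523 |
| 5 | 2 | 0.0815 |
| 6 | 3 | 0.0159 |
| 7 | 3 | 0.0257 |
| 8 | 3 | 0.0381 |
| 9 | 3 | 0.0530 |
| 14 | 4 | 0.0441 |
| 15 | 4 | 0.0556 |
| 20 | 5 | 0.0432 |

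Suspending at 2 of 4 needs c ≥ 0.0523. Not suspending at 3 of 9 needs c just below 0.0530. Any c in that interval gives rows 1–4, 5–8, 9–14 and 15–20 with limits >1, >2, >3 and >4. That matches every printed value except the 6 that opens the third row. Continuing at 3 of 6, 7 or 8 (tails 0.0159 to 0.0381) cannot be squared with suspending at 2 of 4 (0.0523). A typing slip for 9 is the likely explanation, but this is inference.

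**Step 2: operating characteristics.** Exact recursion over 20 independent outcomes, with a look after each patient and suspension when delays exceed the limit r(k):

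| True delay rate | 10% | 20% | 30% |
|---|---|---|---|
| Rows 5–8 and 9–14: ever suspend | 10.4% | 47.2% | 81.6% |
| Same, within first 8 | 7.0% | 26.6% | 51.2% |
| 6–14 governs from patient 6: ever suspend | 9.6% | 45.9% | 80.9% |
| Same, within first 8 | 5.3% | 19.3% | 38.5% |

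**Step 3: chance of meeting the contradiction.** This is P(suspended by patient 8 under the non-overlapping rows) minus P(suspended by patient 4). Nothing is added at patient 5, because a trial still open at 4 has at most 1 delay and so at most 2 at 5.

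- 10%: 0.0700 − 0.0523 = 0.0177
- 20%: 0.2660 − 0.1808 = 0.0852
- 30%: 0.5118 − 0.3483 = 0.1635

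**Step 4: enrolled versus evaluable.** The smallest example is 4 patients with known outcome, 2 of them delayed, and 1 more enrolled. By evaluable count (4) the rule suspends; by enrolled count (5) it does not. The same split occurs with 9 enrolled, 8 evaluable and 3 delays, and with 15 enrolled, 14 evaluable and 4 delays.

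The documents do not give the size of the gap. *Assuming* g enrolled patients without a known evaluable outcome at every look, the limit becomes r(k + g):

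| g | Ever suspend, 10% | Ever suspend, 20% | Within first 8 evaluable, 20% |
|---|---|---|---|
| 0 | 10.4% | 47.2% | 26.6% |
| 1 | 8.1% | 43.8% | 18.7% |
| 2 | 6.4% | 41.0% | 12.4% |
| 3 | 5.3% | 39.1% | 8.2% |

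A second model holds enrolment at 20 and *assumes* each enrolled patient is non-evaluable at random. At a 20% delay rate the chance of suspending is:

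| Non-evaluable | Indexed by enrolled | Indexed by evaluable |
|---|---|---|
| 5% | 43.0% | 44.7% |
| 10% | 38.8% | 42.6% |
| 20% | 30.6% | 39.4% |

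**The case against.** The rows disagree only at exactly 3 delays; with 0 to 2 both continue and with 4 or more both suspend. If any satisfied row triggers suspension, which is a natural reading, the overlap costs nothing. If the laxer row governs, the 20-patient suspension probability moves by about 1 point. Crossing leads to a review that may let accrual continue, and the investigator and the Safety Oversight Committee also monitor the trial. All of this is true. But none of it tells a team with 3 delays among 7 patients which row applies, and the review starts only if the rule is read as triggered.

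The gap figures are scenarios. A constant gap of 3 from the first patient presumes quick accrual, and no accrual rate is given. Section 9.4 defines being on study rather than enrolled, so patients never dosed may not be in the row count. That weakens Section 12.6.3 as a source of the gap. Two sources remain: dosed patients whose surgery window is still open, and exclusions for unrelated delay. The random-exclusion model gives smaller losses, 1.7 and 3.8 points at 5% and 10% non-evaluable, rising to 8.8 points at 20%. The direction is the same under both models.

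Finally, Section 15.5.1.2 does define evaluable next to its table, so the conflict with Section 9.4 bears more on the final proportion than on the monitoring count. That is fair, and the point is secondary here. The two sections still need to agree.

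**Conclusion.** The concern holds. The overlap is plain on the page, and no other section resolves it. The table cannot be applied uniquely at 6, 7 or 8 patients with 3 delays, a state reached with probability 1.8%, 8.5% or 16.3% at true rates of 10%, 20% or 30%. The effect on overall operating characteristics is at most about 1 point, but early detection at a 20% rate could drop by about 7 points (26.6% to 19.3%). Selecting the row by enrolment can only loosen the rule. By how much depends on a gap the documents do not give, so those figures are illustrations.

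The results assume independent outcomes, a look after every patient and, apart from the random-exclusion model, 20 evaluable patients. That the third row should start at 9 is a strong inference from the stated method, not a confirmed fact. Because this is the only numeric suspension threshold and it serves a primary objective, it must be corrected.

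**What to change.** - Check the table against the original toxbdry output. If the output confirms it, change the third row from 6–14 to 9–14.
- Relabel the row column so that it counts evaluable patients with known surgery status (surgery done, or delay declared).
- Reconcile Section 9.4 with Section 15.5.1.2 so that evaluable has one meaning in both the monitoring rule and the final proportion.
- State the crossing probabilities of the confirmed table. With rows 5–8 and 9–14 and 20 evaluable patients they are about 10% at a true delay rate of 10% and about 47% at 20%.

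The cost is two table cells, one reconciled definition and one sentence, with no extra patients or data. Suspension may come slightly earlier than under the enrolled count.

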#### 15.5.1.3. Adverse Events

In addition to feasibility, we will also be monitoring the study for adverse events, both before, during, and after surgery.

Aggregate summaries of adverse events will be generated periodically for study team use, for review by the Safety Oversight Committee, and for submission to ClinicalTrials.gov. Included with these summaries will be a list of all patients experiencing serious adverse events.

Two tabulations will be generated--one that includes all toxicities regardless of attribution, and another that includes only toxicities that are possibly, probably, and definitely related to treatment. For each of these tabulations, the maximum grade (according to CTCAE version 5) of each type of toxicity experienced by each patient will be summarized with frequency distributions. These tabulations will also summarize adverse events by step in the treatment regimen (e.g. neoadjuvant treatment period, surgery / SRS).

For ClinicalTrials.gov, serious adverse events and other adverse events will be summarized separately. These tabulations will reflect the number of patients who experience each type of toxicity regardless of grade or attribution.

As noted in section 15.5.1.2, if the percentage of patients with surgical delay due as a direct or indirect result of ipilimumab and/or nivolumab treatment is elevated, consideration will be given to modifying the immunotherapy treatment regimen. In addition, if the prevalence of adverse events possibly, probably, or definitely related to combination immunotherapy is higher than

anticipated based upon prior experience with this combination, consideration will also be given to modifying the immunotherapy regimen.

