## 9. INVESTIGATIONAL PLAN

### 9.1. Study Design

This is a phase 2 study that assesses the feasibility and efficacy of neoadjuvant immunotherapy in patients with previously untreated, surgically-resectable, solid tumor brain metastases. Histologic types are restricted to those known to extracranially respond to immunotherapy, and will include, but not be limited to, squamous non-small cell lung cancer (NSCLC), non-squamous NSCLC without known

ALK+, EGFR+, and ROS alterations, renal cell carcinoma (RCC), melanoma, and triple negative breast cancer (TNBC) that is PD-L1 positive, ovarian carcinoma, and urothelial carcinoma

Eligible participants will receive a single infusion of nivolumab at a dose of 3 mg/kg and ipilimumab at a dose of 1 mg/kg 7 days ( $\pm$ 3 days) prior to surgical resection of their metastases. Patients will then receive SRS 3 weeks ( $\pm$ 3 weeks) after surgery. Patients will be followed for 18 months after initiating study treatment. Up to 20 participants will be recruited and treated. Blood will be collected periodically during the study for correlative assessments as described in Section [12.7.5](#).

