## 12. SCREENING AND ON-STUDY TESTS AND PROCEDURES

**Table 1: Schedule of Study Tests and Procedures**

Description	Screening	Treatment Period				
	Up to 14 days prior to surgical resection	Neoadjuvant IO	Surgery		Adjuvant SRS 	Follow-up
Week 		-1	1	3 	4	7, 13 +SOC visits
Day 		-10 to -4	1	15	22 ( $\pm$ 3 weeks)	29 + SOC visits
General Evaluations						
Informed Consent	X					
Physical Exam 	X	X	X	X		X
Neurologic Exam 	X	X	X	X		X
Performance Status 	X	X	X	X		X
Adverse Events					Continuous 	
Laboratory Evaluations						
CBC w/diff	X	X 	X	X		X
CMP	X	X 	X	X		X
Thyroid panel	X					X
PT, aPTT	X					
Pregnancy test 	X	X 				
Whole blood for correlative analysis (3x10 mL yellow top) 	X		X 	X	X 	X 
Archival tissue sample 	X					
Surgical tissue sample			X 			
Disease Evaluations						
MRI of the brain 	X					X 
Treatment						
Ipilimumab		X				
Nivolumab		X				
Surgery 			X			
SRS					X	

Number of fractions for SRS treatment will be assigned at physician's discretion

Weeks and days listed are approximate.

Post-operative visit

Clinical evaluations will include a general physical examination, complete neurologic examination, and KPS rating.

Adverse events will be continuously monitored after the first study-mandated agent is administered to the patient and reviewed monthly by the study PI. AE collection will cease 100-days after surgery, or 100 days after ipilimumab/nivolumab infusion for patients who do not undergo surgery.

Only drawn if more than 7-days (24-hours for pregnancy) post screening draw

For women of childbearing potential

Whole blood should be sent to the Substrate Services Core (SSCRS) for processing and then sent to [name] laboratory

Blood should be drawn prior to surgical resection

Blood should be drawn prior to SRS

Drawn only at the week 7 follow-up visit

A sample of archival tissue from the primary or other extracranial tumor will be requested for correlative analysis, if available.

A sample of tissue from the resected metastases will be requested for correlative analysis, if available.

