### 13.1. Adverse Events

An adverse event (AE) is any untoward medical occurrence in a subject receiving study drug and which does not necessarily have a causal relationship with this treatment. For this protocol, the definition of AE also includes worsening of any pre-existing medical condition. An AE can therefore be any unfavorable and unintended or worsening sign (including an abnormal laboratory finding), symptom, or disease temporally associated with the use of nivolumab or ipilimumab, whether or not related to use of nivolumab or ipilimumab. Abnormal laboratory findings that are able to be graded via CTCAE will be collected as AEs and attribution will be reviewed by the PI.

From the time the subject signs the informed consent form until 100-days after surgery, or 100 days after ipilimumab and nivolumab infusion for patients who do not undergo surgery, all AEs must be recorded in the subject medical record and adverse events case report form.

AEs will be assessed according to the CTCAE version 5. If CTCAE grading does not exist for an AE, the severity of the AE will be graded as mild (1), moderate (2), severe (3), life-threatening (4), or fatal (5).

Attribution of AEs will be indicated as follows, with the study drug specified to be ipilimumab, nivolumab, protocol-mandated surgery, or SRS:

- Definite: The AE is clearly related to the study drug
- Probably: The AE is likely related to the study drug
- Possible: The AE may be related to the study drug
- Unlikely: The AE is doubtfully related to the study drug
- Unrelated: The AE is clearly NOT related to the study drug

For additional information on adverse event management algorithms, please see Sections [18.1](#) and [18.2](#) for nivolumab and ipilimumab, respectively.

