### 15.4. Treatments

A CONSORT diagram will be generated that describes flow of treatment. The diagram will provide information about the number of patients who receive

neoadjuvant treatment, undergo surgery (on schedule, late, or not at all), and receive SRS. Details about the SRS administered will be summarized.

The number of patients who receive treatment after SRS will also be tabulated with some detail about the type of treatment administered. Data about maintenance treatment, including the type of immunotherapy, will also be summarized.

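### Adverse events that start after post-SRS maintenance immunotherapy are neither flagged nor tabulated apart, so some may be attributed to the single neoadjuvant dose

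*Combined protocol and SAP*

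**What the plan says.** The protocol regimen contains one dose of each drug, given before surgery: "Eligible participants will receive a single infusion of nivolumab at a dose of 3 mg/kg and ipilimumab at a dose of 1 mg/kg" (Section 9.1). On the later radiosurgery the same section says "Patients will then receive SRS 3 weeks" after surgery, with a window of three weeks either side.

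AE collection continues well past that point. Table 1 says "AE collection will cease 100-days after surgery, or 100 days after ipilimumab/nivolumab infusion for patients who do not undergo surgery", and Section 13.1 requires that, in this period, "all AEs must be recorded in the subject medical record and adverse events case report form". No section ends or marks collection when another anticancer treatment begins.

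Later treatment is expected. Section 15.4 says "The number of patients who receive treatment after SRS will also be tabulated with some detail about the type of treatment administered", and then "Data about maintenance treatment, including the type of immunotherapy, will also be summarized". Section 5.2 describes standard care as resection and SRS followed by maintenance treatment. Sections 9.1 and 11.1 choose histologies for their response to immunotherapy. Section 9.1.5 (concomitant medications) does not restrict later anticancer therapy.

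Attribution in Section 13.1 uses five levels of relatedness, "with the study drug specified to be ipilimumab, nivolumab, protocol-mandated surgery, or SRS". Section 15.5.1.3 plans two tables, one of all toxicities and one of those at least possibly related, each showing the maximum grade of each toxicity type per patient. On timing it adds "These tabulations will also summarize adverse events by step in the treatment regimen (e.g. neoadjuvant treatment period, surgery / SRS". It also says that changing the immunotherapy regimen will be considered if related AEs are more frequent than prior experience suggests.

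**The concern.** The AE tables should let a reader see the toxicity of one neoadjuvant dose followed by surgery and SRS. Much of the collection window comes after that sequence is complete, when patients may be receiving repeated checkpoint inhibitor doses outside the protocol.

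Attribution names a drug and not a dose. If maintenance is nivolumab or ipilimumab, an immune-related event in that period is hard to call unrelated to the earlier dose of the same drug, and a grading of possible is enough to enter the related-only table and the count that feeds reconsideration of the regimen. The named steps give no way to separate such events afterwards. The trial has a single arm, so no concurrent control would reveal the mixing. The related-AE rate could look higher than the protocol regimen itself would produce.

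**Working it through.** The plan gives no figure for this point, so there is none to reproduce. The check is day arithmetic on the windows, followed by a comparison of the sections.

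**Inputs**
- End of AE collection: 100 days after surgery (Table 1; Section 13.1).
- SRS: 3 weeks ± 3 weeks after surgery, i.e. day 0 to day 42, nominal day 21 (Section 9.1).
- Infusion: 7 ± 3 days before surgery, i.e. 4 to 10 days, nominal 7 (Section 9.1).
- Start of maintenance: not given in the documents. Gaps of 0, 4 and 8 weeks after SRS are assumed below.

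**Days of the window after SRS** = 100 − SRS day
- SRS on day 0: 100 − 0 = 100
- SRS on day 21: 100 − 21 = 79
- SRS on day 42: 100 − 42 = 58

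**Share of the window after SRS** = days after SRS ÷ (infusion lead + 100)
- Nominal: 79 ÷ 107 = 74%
- Lowest: 58 ÷ 110 = 53%
- Highest: 100 ÷ 104 = 96%

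These shares count from infusion. Section 13.1 starts recording at consent, which would lengthen the denominator by some days and lower them slightly.

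**Possible overlap with maintenance** = 100 − SRS day − gap

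| SRS day | Gap (assumed) | Overlap, days | Share of 107 days |
|---|---|---|---|
| 21 | 0 weeks | 79 | 74% |
| 21 | 4 weeks | 51 | 48% |
| 21 | 8 weeks | 23 | 21% |
| 42 | 8 weeks | 2 | 2% |

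The overlap can be most of the window or almost nothing, depending on a date that the documents do not give.

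**Weight of one patient**: 1 ÷ 20 = 5 percentage points.

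**Sections side by side**
- Section 15.4 collects the type of post-SRS treatment but does not link it to the AE tables.
- Section 13.1 offers ipilimumab, nivolumab, surgery and SRS as causes, and nothing for other therapy.
- Section 13.1.2 lists how events are categorized in the database (organ system, relationship, grade, resolution). Timing relative to later therapy is not among them.
- Section 15.5.1.3 names steps only as far as surgery / SRS, and neither the related-only table nor the regimen review distinguishes study from non-study dosing.

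**The case against.** The case on the other side is substantial, and most of it stands as a limit on the point.

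- **Attribution is a judgement.** A reader might infer that maintenance toxicity is automatically charged to the neoadjuvant dose. The documents do not say so. Relatedness is judged against the study drug, and an investigator may grade an event unlikely or unrelated, which keeps it out of the related-only table. Only the all-toxicity and ClinicalTrials.gov tables include such events automatically, and they make no causal claim. What remains is repeat dosing with the same drug or class, where the judgement is hard.
- **The step list is illustrative.** A later step is unspecified, not excluded.
- **Maximum grade is per toxicity type.** A severe event on maintenance can displace a lower earlier grade only for the same type, and the planned split by step may already prevent that.
- **The regimen review is soft.** It has no threshold and leads only to consideration. The one numerical rule, for surgical delay (Section 15.5.1.2), is settled before SRS and is unaffected.
- **Safety is not a listed objective** in Section 8; the AE tables are descriptive monitoring.
- **Truncation would have a price.** Ending the main related table at the first non-protocol therapy would hide delayed toxicity of the study dose. That is a good reason not to truncate, but it does not argue against showing later events separately.

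A reader might also put a number on the excess from the 25-37% severe immune-related rate that Section 9.1.3 quotes for ipilimumab. If 10 of 20 patients received ipilimumab-containing maintenance, that gives 10 × 0.25 to 10 × 0.37 = 2.5 to 3.7 events, or 12.5 to 18.5 points. The documents do not support this as an estimate. The rate comes from advanced melanoma, while uptake and drug are assumed. The sum also takes the whole rate to fall inside the window, every event to be misattributed, and none of these patients to have had an earlier severe event.

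**Conclusion.** The point holds as a gap in the plan: events on maintenance nivolumab or ipilimumab may be attributed to the single neoadjuvant dose and raise the related-AE rate, and the tables as specified need not reveal it. Between 58 and 100 of the 100 post-surgery collection days fall after SRS (79 at nominal timing). How many are spent on maintenance, and by how many patients, cannot be known from the documents, so the size of any bias is unknown.

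The conclusion assumes that some patients start maintenance with the same drugs or class inside the window, which Section 15.4 makes plausible but does not quantify. It does not show that the plan prescribes misattribution or that the regimen would be changed wrongly. It leaves both primary endpoints untouched. This is a cheap improvement to the safety reporting.

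**What to change.** 1. On the case report form, record the start date of the first non-protocol systemic anticancer therapy, next to the post-SRS treatment data already planned under Section 15.4.
2. In Section 13.1, add non-protocol systemic therapy to the attribution options.
3. In Section 15.5.1.3, name a third tabulation step for events that start after that date, and state that maximum grade per toxicity type is computed within each step.
4. Keep the full-window all-toxicity, related-only and ClinicalTrials.gov tables. When the study team and the Safety Oversight Committee review related AEs, show them with and without the third step. Do not truncate the main table, and leave the regimen-modification rule as it is.

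The attribution option alone will not resolve a doubtful case. The date-based step does most of the work, because it needs no causal judgement.

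Cost: one date, one attribution option and a few sentences of SAP text. The small downside is that a late event truly due to the study dose may appear in the third step; it stays visible in the full-window tables.
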